11. REGULATORY AND REPORTING REQUIREMENTS

The entities providing oversight of safety and compliance with the protocol require reporting as outline below.

The Washington University Human Research Protection Office (HRPO) requires that all events meeting the definition of unanticipated problem or serious noncompliance be reported as outlined in Section 11.2.

11.1. Definitions

11.1.1. Adverse Events (AEs)

Definition: any unfavorable medical occurrence in a human subject including any abnormal sign, symptom, or disease.

Grading: the descriptions and grading scales found in the revised NCI Common Terminology Criteria for Adverse Events (CTCAE) version 4.0 will be utilized for all

toxicity reporting. A copy of the CTCAE version 4.0 can be downloaded from the CTEP website.

Attribution (relatedness), Expectedness, and Seriousness: the definitions for the terms listed that should be used are those provided by the Department of Health and Human Services' Office for Human Research Protections (OHRP). A copy of this guidance can be found on OHRP's website:

http://www.hhs.gov/ohrp/policy/advevntguid.html

11.1.2. Serious Adverse Event (SAE)

Definition: any adverse drug experience occurring at any dose that results in any of the following outcomes:

- o Death
- A life-threatening adverse drug experience
- Inpatient hospitalization or prolongation of existing hospitalization
- A persistent or significant disability/incapacity (i.e., a substantial disruption of a person's ability to conduct normal life functions)
- A congenital anomaly/birth defect
- Any other experience which, based upon appropriate medical judgment, may jeopardize the subject and may require medical or surgical intervention to prevent one of the outcomes listed above

11.1.3. Unexpected Adverse Experience

Definition: any adverse drug experience, the specificity or severity of which is not consistent with the current investigator brochure (or risk information, if an IB is not required or available).

11.1.4. Life-Threatening Adverse Experience

Definition: any adverse drug experience that places the subject (in the view of the investigator) at immediate risk of death from the reaction as it occurred, i.e., it does not include a reaction that, had it occurred in a more severe form, might have caused death.

11.1.5. Unanticipated Problems

Definition:

- unexpected (in terms of nature, severity, or frequency) given (a) the research procedures that are described in the protocol-related documents, such as the IRB-approved research protocol and informed consent document; and (b) the characteristics of the subject population being studied;
- related or possibly related to participation in the research ("possibly related" means there is a reasonable possibility that the incident, experience, or outcome may have been caused by the procedures involved in the research); and
- suggests that the research places subjects or others at a greater risk of harm (including physical, psychological, economic, or social harm) than was previously known or recognized.

11.1.6. Noncompliance

Definition: failure to follow any applicable regulation or institutional policies that govern human subjects research or failure to follow the determinations of the IRB. Noncompliance may occur due to lack of knowledge or due to deliberate choice to ignore regulations, institutional policies, or determinations of the IRB.

11.1.7. Serious Noncompliance

Definition: noncompliance that materially increases risks, that results in substantial harm to subjects or others, or that materially compromises the rights or welfare of participants.

11.1.8. Protocol Exceptions

Definition: A planned deviation from the approved protocol that are under the research team's control. Exceptions apply only to a single participant or a singular situation.

Pre-approval of all protocol exceptions must be obtained prior to the event.

11.2. Reporting to the Human Research Protection Office (HRPO) at Washington University

The PI is required to promptly notify the IRB of the following events:

- Any unanticipated problems involving risks to participants or others which occur at WU, any BJH or SLCH institution, or that impacts participants or the conduct of the study.
- Noncompliance with federal regulations or the requirements or determinations of the IRB.
- Receipt of new information that may impact the willingness of participants to participate or continue participation in the research study.

These events must be reported to the IRB within 10 working days of the occurrence of the event or notification to the PI of the event. The death of a research participant that qualifies as a reportable event should be reported within 1 working day of the occurrence of the event or notification to the PI of the event.

11.3. Reporting to the Quality Assurance and Safety Monitoring Committee (QASMC) at Washington University

The PI is required to notify the QASMC of any unanticipated problem occurring at WU or any BJH or SLCH institution that has been reported to and acknowledged by HRPO as reportable. (Unanticipated problems reported to HRPO and withdrawn during the review process need not be reported to QASMC.)

QASMC must be notified within **10 days** of receipt of IRB acknowledgment via email to a QASMC auditor.

11.4. Timeframe for Reporting Required Events

Adverse events will be tracked for 60 minutes after each lidocaine infusion. For the purposes of this protocol, all adverse events will be collected and documented on CRFs, except the following adverse effects, which are likely to be associated with mFOLFOX6 treatment, and are unlikely to be associated with lidocaine treatment:

- Nausea and Vomiting
- Diarrhea
- Stomatitis
- Hematologic toxicity, e.g. neutropenia
- Loss of appetite
- Fatigue
- Constipation
- Fever
- Generalized pain
- Cough
- Temporary increase in liver functions
- Arthralgia
- Myalgia
- Hair loss

The treatment with 5-FU has been associated with cardiotoxicity in 6-8.5% of colorectal cancer patients receiving FOLFOX chemotherapy [46, 47], particularly due to prolonged (24-hour) infusion of 5-FU. Symptoms of cardiac toxicity appearing later than 1 hour after lidocaine infusion may be attributable to this effect of 5-FU.

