1.5. Preliminary Data

The proposed study is to test, for the first time, the tolerability of intravenous lidocaine intervention in this group of patients undergoing oxaliplatin-based chemotherapy for colorectal cancer. The starting dose regimen of lidocaine in this study (as detailed in Table 1) was derived from intravenous lidocaine pharmacokinetic data from our previously completed study [32]. Maximum plasma concentrations (Cmax) above $3.3 \mu g/mL$, obtained with 5mg/kg (true body weight) 30-min infusion of lidocaine, resulted in peak concentration-related temporary side effects (dizziness, perioral numbness, dry mouth, blurred vision), especially in overweight patients. In a modified dosing regimen of 5mg/kg Ideal Body Weight (IBW) lidocaine (infused over 40 minutes) that we use in an ongoing clinical trial (NCT02363803) to target Cmax below $3\mu g/mL$, minimal side effects have been observed. In the proposed dose regimen for this study, we will be targeting lidocaine plasma Cmax of approximately 2.5 $\mu g/mL$. This will be obtained with an initial brief infusion of 1.0 mg/kg IBW over 10 minutes, and a 0.04 mg/kg/min infusion over additional 120 minutes, which was derived using non-parametric pharmacokinetic modeling (WinNonlin, Pharsight, CA).

Lidocaine treatment will start 10 minutes prior to oxaliplatin 120-minute infusion. Oxaliplatin alpha-elimination half-life is about 20 minutes; therefore, one hour after infusion the plasma concentration drops by more than 85% [39]. The longer half-life of lidocaine (90-120 min) is expected to provide sufficient plasma concentrations (>1 μ g/mL) for at least two hours after oxaliplatin treatment, to prevent the peak concentration-dependent toxicity of oxaliplatin on the peripheral nerves.

2. **OBJECTIVES**

1. To determine the tolerability (defined as lack of dose-limiting toxicity – see section 6.4.2) of lidocaine co-infusion in colorectal cancer patients treated with oxaliplatin.

2. To determine the initial efficacy of intravenous lidocaine as a systemic voltage-gated sodium channel (Nav) blocker in preventing oxaliplatin-induced peripheral neuropathy.

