6.4.2. Dose-Limiting Toxicities

Dose limiting criteria for lidocaine include the appearance of any of the following effects during the study drug infusion or up to 60 minutes thereafter:

- Any of the following cardiac arrhythmias:
- Atrial Fibrillation Grade 3+
- Atrial flutter, Grade 3+
- Asystole, any
- Cardiac arrest
- Atrioventricular (AV) block, Grade 3+
- Paroxysmal atrial tachycardia, Grade 2+
- Sinus bradycardia, Grade 2+
- Sinus tachycardia, Grade 3+
- Ventricular arrhythmia, Grade 2+
- Ventricular fibrillation, any
- Seizure, any
- Dizziness, Grade 3+
- Somnolence, Grade 3+
- Syncope, any
- Blurred vision, Grade 3
- Occurrence of any other Grade 3 or higher adverse effect thought to be at least probably associated with lidocaine treatment.

In addition, a dose-limiting toxicity will be an evidence of unanticipated disease progression based on a routinely performed CT, PET or MRI scan (as indicated, and interpreted by the treating physician) at 8 weeks after oxaliplatin initiation – i.e. 4 cycles of treatment. This may indicate that the study drug negatively affects the efficacy of mFOLFOX6 chemotherapy.

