6.5. Toxicity and DLT Evaluations

All patients who receive any study treatment are evaluable for toxicity. Patients are evaluated from first receiving any study treatment until 60 minutes following end of each infusion of lidocaine. There are no concerns with concentration-independent toxicity of lidocaine with intermittent administration such as in this study.

DLT, also defined as drug dose that interferes with oxaliplatin efficacy or otherwise unanticipated disease progression, will be assessed by a CT, PET or MRI scan at 8-weeks, or as clinically indicated .

A patient is evaluable for DLT assessment only if enrolled in the dose-finding portion of the study.

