8. STUDY CALENDAR

Requi red Assess ment	Baseli ne visit		Treatme	nt visit #	6 th cycle F-U° Toler ability phase	8-10 week F-U	1 year F-U	2 year F-U					
								Rando ph					
		1	2	3	4	5	6	7	8				
Infor med Conse nt	V												
Inclus ion/e xclusi on criteri	V							\langle					
a Blood tests*	\checkmark	\checkmark		\checkmark			\checkmark						
Blood sampl e for genot yping		V											
Electr ocardi ogram (ECG) **	V	V	V	V	√	✓	V	V	V				
Rando mizati on	V			X									
Demo graph ic data collect ion	V												
RAND -12 and BPI questi onnai res	~							V		V	V		
Cognit ive testin g	V										V		
HADS questi onnai re	V												

NPSI questi onnai	V	V	V	V	\checkmark	V	V	V	V	V	V		
re Senso ry mappi	V	V	V	√	V	V	√	V	V	√	V		
ng QST** *	\checkmark			\checkmark				\checkmark		\checkmark	\checkmark		
Cold allody nia and dysest hesia	V	V	V	V	V	V	V	V	V	V	V		
PN gradi ng	V	V	V	V	\checkmark	V	V	V	\checkmark	V	V		
Study drug admin istrati on		V	V	V	V	V	V		V				
QLQ- CIPN2 0 assess ment		V	V	V	V	V	V	V	V	V	V		
Adver se effect monit oring ‡		V	V	V	V	Ň	V	V	V				
Serial blood sampl ing for PK*** *		V	V										
Single PK sampl e - at 130mi n				V	V	V	V	V	V				
Progr ession -free and overal l surviv al (medi cal												V	V
recor d													

ſ	revie							
	w)							

*Comprehensive metabolic panel (CMP). **ECG will be performed at baseline (12-lead) and monitored during study sessions (3-lead). *** For subjects participating at the satellite locations, the CPT test will not be performed. ‡ Adverse effects will be monitored during and 60 min after the study drug infusion. **** Serial blood sampling for PK collected during first 2 cycles of study drug, then a single PK sample at the remaining cycles. °A scheduled follow-up visit 2 weeks after the 6th treatment visit (immediately prior to the 7th) for patients in the tolerability phase. °° 8-10 weeks after the last cycle (or 12th, whichever earlier), an additional visit will be planned. BPI=Brief Pain Inventory. HADS = Hospital Anxiety and Depression Scale; NPSI = Neuropathic Pain Symptom Inventory; QST = Quantitative Sensory Testing; PK = Pharmacokinetics

9. **OBSERVATIONS AND MEASUREMENTS**

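### Adverse events are collected only to 60 minutes after each infusion, so later serious events are not systematically recorded and a between-arm safety comparison would be incomplete

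*Combined protocol and SAP*

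**What the plan says.** Four places in the protocol give the same collection window:

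- Section 11.4: "Adverse events will be tracked for 60 minutes after each lidocaine infusion".
- Section 6.5, toxicity evaluation: "Patients are evaluated from first receiving any study treatment until 60 minutes following end of each infusion of lidocaine".
- Section 6.4.2, dose-limiting toxicities: effects that appear "during the study drug infusion or up to 60 minutes thereafter".
- Section 8, calendar footnote: "Adverse effects will be monitored during and 60 min after the study drug infusion". As far as the extracted table can be read, this row is marked at treatment visits only, not at follow-up.

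Section 1.5 expects lidocaine to stay above 1 µg/mL "for at least two hours after oxaliplatin treatment, to prevent the peak concentration-dependent toxicity of oxaliplatin on the peripheral nerves".

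Section 11.1.2 defines SAEs by outcome, including "Inpatient hospitalization or prolongation of existing hospitalization", but no section gives a period over which SAEs are collected. Section 11.4 also keeps a list of expected chemotherapy effects off the CRF (neutropenia, fever, vomiting and diarrhoea among them), with no exception for grade or seriousness. It then says: "Symptoms of cardiac toxicity appearing later than 1 hour after lidocaine infusion may be attributable to this effect of 5-FU".

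Section 12 has the principal investigator and the research coordinator watch for serious toxicity throughout, and report adverse events once they learn of them. Sections 9 and 10 plan no safety comparison between the randomised arms.

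**The concern.** Section 1.5 describes this as the first test of lidocaine given with oxaliplatin chemotherapy in these patients. The randomised, double-blind phase is the only part with a concurrent control, so it is where an unexpected toxicity of the combination could best be seen.

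Structured collection ends while the plan's own pharmacokinetics still predict a substantial lidocaine level, and does not resume before the next infusion. A serious event that night or a week later reaches the trial only if someone on the study team hears of it. Events found that way tend to be under-counted, and nothing ensures that the same question is asked of every patient.

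The cardiac sentence adds to this. Its one-hour boundary is also where tracking ends, so the events it suggests may be due to 5-FU are the ones the CRF does not collect.

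**Working it through.** **Inputs**

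- Target peak about 2.5 µg/mL and half-life 90–120 min (section 1.5).
- Lidocaine runs 10 + 120 = 130 min. Oxaliplatin starts at 10 min and runs 120 min, so both end at 130 min (sections 1.5 and 6.2).
- Section 5 treats the 130-minute sample as the peak.
- Assumption: single-exponential decline from that peak. This is a simplification, since the plan derived its regimen by non-parametric modelling.

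**Formula:** C(t) = 2.5 × 0.5^(t/h), with t in minutes after the end of infusion and h the half-life.

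**Reproducing the plan's own figure (t = 120)**

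- h = 90: 2.5 × 0.5^(120/90) = 0.99 µg/mL
- h = 120: 2.5 × 0.5^(120/120) = 1.25 µg/mL

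The statement of more than 1 µg/mL for two hours reproduces, apart from a shortfall of about one minute at the shortest half-life.

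**Level when tracking stops (t = 60)**

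- h = 90: 2.5 × 0.5^(60/90) = 1.57 µg/mL, 63% of peak
- h = 120: 2.5 × 0.5^(60/120) = 1.77 µg/mL, 71% of peak

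**Time to reach 1 µg/mL:** h × ln(2.5)/ln(2)

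- h = 90: 119 min; h = 120: 159 min
- Tracking therefore stops 119 − 60 = 59 to 159 − 60 = 99 min before that point.

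**Share of the cycle covered**

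- Tracked time is 130 + 60 = 190 min of 14 × 1,440 = 20,160 min, or 0.94%.
- This is coverage for any serious event, not lidocaine exposure. Five half-lives take 5 × 90 = 450 min to 5 × 120 = 600 min (7.5–10 h).
- The continuous 5-FU infusion lasts 46 h (section 6.2). Whenever it starts, at least 46 − 190/60 = 42.8 h of it lies outside the tracked time.

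**What a comparison could show**

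- Section 11.4 cites 5-FU cardiotoxicity in 6–8.5% of patients. With 15 per arm that is 15 × 0.06 = 0.9 to 15 × 0.085 = 1.3 expected events per arm.
- Against 1/15, Fisher's exact two-sided test gives p = 0.08 for 6/15 and p = 0.035 for 7/15. Seven events in one arm would be needed for nominal significance.

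**What the other safety provisions supply**

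- Section 12: reporting that depends on awareness, with no visit question, CRF field or tabulation by arm.
- Section 11.2: unanticipated problems, which section 11.1.5 limits to unexpected and at least possibly related events, and reportable deaths.
- Sections 6.2 and 6.11: follow-up of adverse effects already identified.
- Sections 6.11 and 9.2: progression and survival at one and two years by record review, which does not capture non-fatal SAEs.

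None of these asks every patient, at a set time, about serious events since the last visit.

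**The case against.** The best defence is that the window fits the drug. Section 6.5 gives the reason: concentration-independent toxicity is not a concern with intermittent dosing. Section 1.5 ties side effects to peaks above 3.3 µg/mL. The level at 60 minutes is 1.57/3.3 = 48% to 1.77/3.3 = 54% of that and falling. This stands as a limit on risk: a new peak-related lidocaine effect after one hour is less likely. It does not cover interactions with the chemotherapy or serious events of unknown cause. Section 6.2 also restricts driving for three hours after the infusion, so the plan itself allows for effects beyond one hour.

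Four stronger readings are tempting, and the documents do not support them.

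- A reader might infer that later serious events cannot be compared at all. Sections 11.2 and 12 allow reporting with no 60-minute limit. Deaths and progression are collected in both arms, and section 6.2 documents every chemotherapy dose change. Known events could be tabulated by arm; the table would be incomplete.
- A reader might infer that late cardiac events are assigned to 5-FU by rule. Section 11.4 says only that they may be attributable to it. It is a presumption, though one that could steer such events away from the related-event test in section 11.1.5.
- A reader might infer that 1 µg/mL marks a toxic level. Section 1.5 uses it as a level sufficient for nerve protection.
- A reader might infer that objective 1 fails. Section 2 defines tolerability as absence of DLT, and section 6.3 tests it in the open-label phase of eight patients, which has no arms to compare. Loss of chemotherapy efficacy is checked there by scan at eight weeks (sections 6.4.2 and 6.5).

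Nor would randomisation settle the cause of cardiac events. Section 6.2 lets the 5-FU bolus be omitted in metastatic patients, section 4.4 has no stratification, and about one event per arm is expected.

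**Conclusion.** The point holds in a limited form and should be addressed. Structured collection ends at 60 minutes, when the plan's own figures imply about 1.6–1.8 µg/mL, or 63–71% of the target peak. No section provides systematic collection of SAEs after that. Following the plan as written would give a between-arm account of later serious events that rests on what staff happened to learn, and is therefore incomplete.

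The concentrations rest on the target peak being reached at 130 minutes and on single-exponential decline. The gap in collection does not depend on either. The documents give no rate or timing for SAEs, so the number that would be missed cannot be estimated. Sample size, power and the primary efficacy analysis are unaffected.

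**What to change.** 1. Reconcile section 11.4 (tracking ends at 60 minutes) with section 12 (continuous monitoring of serious toxicity), and state the SAE collection period.
2. Keep the 60-minute window for DLTs and minor events.
3. At each existing two-week visit and the 8–10 week visit, record in both randomised arms, with onset time, all SAEs as defined in section 11.1.2 since the last visit, and Grade 3+ events not on the section 11.4 exclusion list.
4. State that an event on that list is still recorded when it meets the SAE definition.
5. Replace the 5-FU sentence with a statement that late cardiac events are recorded with onset time and reported by arm, without advance attribution.
6. Add to section 10 a descriptive table of these events by arm, with no significance test.

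No new visits are needed. The cost is one question and a short CRF page at up to 30 × 8 = 240 randomised treatment visits, plus the follow-up visit, with grading of whatever is reported. Leaving non-serious listed effects off the CRF keeps this small, since routine chemotherapy toxicity need not be recorded. The table will describe late serious events; with 15 patients per arm it will not establish their cause.

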6.11. Duration of Follow-up

In the tolerability phase, patients will have a follow-up visit prior to their 7th cycle of mFOLOFX6, and an additional visit at 8-10 weeks after 12th (or last, whichever is earlier) dose of oxaliplatin. In the randomized phase, patients will have a follow-up visit at 8-10 weeks after 12th (or last, whichever is earlier) dose of oxaliplatin. The main purpose of these visits is to compare the development of persistent neuropathy and neuropathic pain between the two study arms. Patients removed from study for unacceptable adverse events will be followed until resolution or stabilization of the adverse event. One year and again at two years after enrollment in the study, progression-free and overall survival will be assessed by review of the medical record.

7. **DOSE MODIFICATIONS**

In case of mild (Grade 1 AE) tachy- or brady- arrhythmias, or oxygen desaturation, the infusion will be paused, and attempted to resume 10 minutes after resolution of the adverse effect. In any case of moderate (Grade 2+) to severe tachy- or brady- arrhythmias (except sinus tachycardia, which is defined as DLT if Grade 3+), or oxygen desaturation, the infusion will be stopped, and patient withdrawn from the study.

In any case of serious side effects, the study team will follow the American Society of Regional Anesthesia (ASRA) guidelines on systemic local anesthetic toxicity [43]. Intralipid[®] infusion for possible local anesthetic systemic adverse effect management will be readily available and carried by the study the team.

The following stopping rules will be applied:

Lidocaine is not known to affect liver or kidney function. However, if the subject develops renal insufficiency (Creatinine clearance <30 ml/min) or liver insufficiency (ALT or AST >3 times upper normal value in patients with no liver metastases, ALT or AST >5 times upper normal value in patients with liver metastases) for any reason, the study drug will not be administered at that oxaliplatin treatment session for safety reasons. If prior to subsequent cycles of chemotherapy the limiting kidney/liver function improves beyond the above criteria, the study drug can be administered with oxaliplatin, within the same mFOLFOX6 regimen.

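### Section 11.4 keeps 14 event types off the CRF at any grade or seriousness, so an event that 6.4.2 could count as a DLT may have no CRF record

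*Combined protocol and SAP*

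**What the plan says.** - **CRF rule (11.4).** Events are tracked until 60 minutes after each lidocaine infusion. Within that, "all adverse events will be collected and documented on CRFs, except the following adverse effects", described as effects "which are likely to be associated with mFOLFOX6 treatment, and are unlikely to be associated with lidocaine treatment". The list runs from "Nausea and Vomiting" to hair loss and includes "Temporary increase in liver functions". It states no grade ceiling, makes no exemption for serious events, and draws no distinction by phase or arm.
- **DLT definition (6.4.2).** After the named cardiac and neurological events comes a catch-all: "Occurrence of any other Grade 3 or higher adverse effect thought to be at least probably associated with lidocaine treatment". The window is the infusion and the following 60 minutes.
- **Use of the DLT count (6.3, 6.4.3, 6.5).** Three or more of 8 patients with a DLT leads to the next lower dose level; fewer opens the randomised phase. Only patients in the dose-finding part are evaluable for DLT.
- **Liver hold (section 7).** With "ALT or AST >3 times upper normal value in patients with no liver metastases", or more than 5 times in patients with liver metastases, "the study drug will not be administered at that oxaliplatin treatment session for safety reasons". Study drug may be given again at a later cycle once values improve.
- **Monitoring report (section 12).** The semi-annual report must contain toxicities by cohort, the number of DLTs, and the number of participants who met early stopping rules.

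**The concern.** The exception fixes attribution by event type before any event has been seen. Section 11.1.1 prescribes CTCAE grading for all toxicity reporting and refers to standard definitions of relatedness and seriousness, but for the listed types the CRF would hold nothing to grade or attribute.

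Two things are at stake. First, tolerability is Objective 1 and is defined as lack of DLT. The dose decision turns on a count of three patients, so one event without a CRF record can matter. Second, the randomised phase is the only place where severe events around the infusion can be set against placebo, and for these 14 types the adverse-event data would not hold them.

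**Working it through.** The plan gives no figure on this point to reproduce. The check is a comparison of sections, with two small calculations for scale.

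**1. Count.** Taking nausea and vomiting as one bullet, 11.4 lists: nausea/vomiting, diarrhoea, stomatitis, haematologic toxicity, loss of appetite, fatigue, constipation, fever, generalised pain, cough, temporary liver rise, arthralgia, myalgia, hair loss. That is 14.

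**2. DLT against CRF.**

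| Feature | 6.4.2 catch-all | 11.4 exception |
|---|---|---|
| Event type | any other | 14 listed types |
| Grade | 3 or higher | any |
| Attribution | judged per event, at least probable | presumed unlikely, by type |
| Window | infusion + 60 min | tracked to 60 min after infusion |
| Result | counts toward 3 of 8 | no CRF entry |

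The windows coincide, so the overlap is possible. It needs a listed type, Grade 3 or higher, arising in the window, and judged at least probably due to lidocaine.

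**3. What a lost DLT would do (illustration).** Let p be a patient's chance of having a DLT and f the share of such patients whose only DLT is unrecorded and therefore uncounted. Neither value is in the documents; both are assumptions. The chance of reaching the de-escalation trigger is P(X ≥ 3) with X ~ Binomial(8, p(1 − f)):

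| p | f = 0 | f = 10% | f = 25% | f = 50% |
|---|---|---|---|---|
| 20% | 0.203 | 0.161 | 0.105 | 0.038 |
| 30% | 0.448 | 0.372 | 0.260 | 0.105 |
| 40% | 0.685 | 0.596 | 0.448 | 0.203 |
| 50% | 0.855 | 0.780 | 0.630 | 0.321 |

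At p = 30%, losing a quarter of DLTs lowers the chance from 0.448 to 0.260. This is an upper reading of the harm, since an event missing from the CRF may still be noticed and counted.

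**4. Liver hold.** Section 7 acts on laboratory values, which come from the metabolic panel (6.1 and the section 8 calendar), not from an event form. Because study drug may resume on improvement, a rise that triggers a hold can prove temporary and so be of the excepted kind. Section 11.4 does not define temporary, and it cannot be known on the day of the hold. Section 6.2 puts mFOLFOX6 dose changes on the CRF and 6.10 puts reasons for discontinuing protocol therapy there. No section found asks for a single held study-drug dose and its ALT/AST trigger.

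**5. What a comparison by arm could show.** With 30 randomised 1:1, about 15 per arm, two-sided Fisher tests give:
- 0/15 against 4/15: 2 × C(15,4)/C(30,4) = 2 × 1365/27405 = 0.10
- 0/15 against 5/15: 2 × C(15,5)/C(30,5) = 2 × 3003/142506 = 0.04

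Only a very large imbalance would stand out.

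**The case against.** The case for leaving 11.4 alone has real force.

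- **The clause on attribution could be read as a condition.** On that reading an event judged probably due to lidocaine falls outside the exception, and the conflict with 6.4.2 goes away. Grammatically, though, the clause describes the listed types and asks for no judgement on each event. If the condition was meant, the text should say so.
- **The tracking window already excludes most of these events.** Neutropenia, stomatitis or hair loss would mostly arise between visits, and deleting the list would not bring them in. This stands, and it limits what the fix can deliver.
- **Other safeguards exist.** In the dose-finding phase the investigator reviews all patient data at least monthly, serious toxicities are monitored continuously and reported under institutional guidelines, and DLT numbers go to the monitoring committee (section 12). These make it less likely that a DLT is overlooked. They do not create a CRF record or a tabulation by arm.
- **The liver rule is covered.** Section 7 presents the hold as a stopping rule, and section 12 asks for counts of participants meeting early stopping rules. On a natural reading, liver-triggered holds are therefore reported. This largely stands.
- **Omitting expected background toxicity in a 30-patient pilot is a reasoned choice.** This holds for mild events. It does not explain the absence of a limit by grade or seriousness.

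**Conclusion.** The point holds in a limited form. Sections 11.4 and 6.4.2 do not fit together: 14 types are exempt from the CRF at any grade, while the DLT catch-all exempts none. The consequence for the 3-of-8 rule is possible rather than certain, and it concerns only the single-arm tolerability phase. In the randomised phase the gap is the missing adverse-event record for severe or serious listed events within the tracking window. That it affects both arms is inferred from the absence of any distinction by arm.

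A reader might infer more, and the documents do not support it:

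- **That a between-arm difference in these events cannot be estimated at all, or that the data are thrown away.** ALT and AST are measured by the panel, pain is scored at each treatment day (9.2), and chemotherapy dose changes go on the CRF.
- **That 11.4 contradicts the liver hold.** The hold runs on laboratory values, and only temporary rises are excepted. What is missing is an event record.
- **That the placebo arm was meant to test for altered chemotherapy toxicity.** The worry stated in 6.4.2 is loss of mFOLFOX6 efficacy, which the plan addresses with scans and survival. The randomised phase is there to assess prevention of neuropathy.

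**What to change.** 1. In 11.4, limit the exception to Grade 1-2, non-serious events that are not judged at least probably related to lidocaine.
2. Record on the CRF every Grade 3 or higher or serious event of the 14 types, and each study-drug hold triggered by ALT/AST with the value that triggered it.
3. Summarise these by arm, descriptively, in the randomised phase, and by cohort in the tolerability phase.
4. Reconcile 6.4.2, 7, 11.4 and 12, so that whatever can count as a DLT or trigger a hold has a record behind the count sent to the monitoring committee.
5. Decide whether chemotherapy toxicity by arm is wanted. With the 60-minute window unchanged, items 1 to 3 capture mainly events around the infusion. To describe more, Grade 3 or higher or serious listed events between cycles would have to be taken from routine oncology records at the next visit.

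This changes recording only and leaves the clinical rules as they are. Items 1 to 4 cost a few more CRF entries; item 5 adds a short record check at each visit. The return is a more complete safety record and DLT count. It does not give a powered comparison of the arms.
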